11.10.9. Safety Figures

Safety: Figures						
No.	Population	IDSL / Example Shell	Title	Programming Notes	Report at Interim	Report at Final
Laboratory						
3.1.	SPDB		Scatter Plot of Week12/Withdrawal vs. Baseline for Chemistry	IDSL	Y	
3.2.	SPDB		Scatter Plot of Week12/Withdrawal vs. Baseline for Hematology	IDSL	Y	

CONFIDENTIAL

204948

11.10.10. ICH Listings

ICH : Listings						
No.	Population	IDSL / TST ID / Example Shell	Title	Programming Notes	Report at Interim	Report at Final
Subject Disposition						
1.	Screened	ES7	Listing of Reasons for Screen Failure	Journal Guidelines	Y	
2.	FAS1	ES2	Listing of Reasons for Study Withdrawal	ICH E3	Y	Y
3.	FAS1	BL1	Listing of Subjects for Whom the Treatment Blind was Broken	ICH E3	Y	Y
4.	FAS1	TA1	Listing of Planned and Actual Treatments	IDSL	Y	
Protocol Deviations						
5.	FAS1	DV2	Listing of Important Protocol Deviations	ICH E3	Y	Y
6.	FAS1	IE3	Listing of Subjects with Inclusion/Exclusion Criteria Deviations	ICH E3	Y	Y
Populations Analysed						
7.	Enrolled	SP3	Listing of Subjects Excluded from Any Population	ICH E3	Y	Y
Demographic and Baseline Characteristics						
8.	FAS1	DM2	Listing of Demographic Characteristics	ICH E3	Y	
9.	FAS1	DM2	Listing of Baseline Disease Characteristics		Y	
10.	FAS1	DM9	Listing of Race	ICH E3	Y	
Current and Past Medical Conditions, Prior and Concomitant Medications						
11.	FAS1	MH2	Listing of Medical Conditions		Y	Y
12.	FAS1	CM3	Listing of Concomitant Medications	IDSL	Y	Y

CONFIDENTIAL

204948

ICH : Listings						
No.	Population	IDSL / TST ID / Example Shell	Title	Programming Notes	Report at Interim	Report at Final
13.	FAS1	CM3	Listing of Prior or Concomitant NDO Medications	IDSL	Y	
Exposure and Treatment Compliance						
14.	FAS1	EX3	Listing of Exposure Data	ICH E3	Y	Y
Adverse Events						
15.	SPDB	AE8	Listing of All Adverse Events	ICH E3	Y	Y
16.	SPDB	AE7	Listing of Subject Numbers for Individual Adverse Events	ICH E3	Y	Y
17.	SPDB	AE2	Listing of Relationship Between Adverse Event System Organ Classes, Preferred Terms, and Verbatim Text	IDSL	Y	Y
Serious and Other Significant Adverse Events						
18.	SPDB	AE8	Listing of Fatal Serious Adverse Events	ICH E3	Y	Y
19.	SPDB	AE8	Listing of Non-Fatal Serious Adverse Events	ICH E3	Y	Y
20.	SPDB	AE14	Listing of Reasons for Considering as a Serious Adverse Event	ICH E3	Y	Y
21.	SPDB	AE8	Listing of Adverse Events Leading to Withdrawal from Study / Permanent Discontinuation of Study Treatment	ICH E3	Y	Y
22.	SPDB	AE8	Listing of Special Interest Adverse Events	ICH E3	Y	Y
Hepatobiliary (Liver)						
23.	SPDB	MH2	Listing of Medical Conditions for Subjects with Liver Stopping Events	IDSL	Y	Y
24.	SPDB	SU2	Listing of Substance Use for Subjects with Liver Stopping Events	IDSL	Y	Y
25.	SPDB	LIVER5	Listing of Liver Monitoring/Stopping Event Reporting	IDSL	Y	Y

CONFIDENTIAL

204948

ICH : Listings						
No.	Population	IDSL / TST ID / Example Shell	Title	Programming Notes	Report at Interim	Report at Final
26.	SPDB	LIVER6	Listing of Liver Stopping Event Information for RUCAM Score	IDSL	Y	Y
27.	SPDB	LIVER7	Listing of Liver Biopsy Details	IDSL	Y	Y
28.	SPDB	LIVER8	Listing of Liver Imaging Details	IDSL	Y	Y
29.	SPDB	LIVER13	Listing of Subjects Meeting Hepatobiliary Laboratory Criteria Post-Baseline	IDSL	Y	Y
All Laboratory						
30.	SPDB	LB5	Listing of All Laboratory Data for Subjects with Any Value Outside Normal Range	ICH E3	Y	Y

CONFIDENTIAL

204948

11.10.11. Non-ICH Listings

Non-ICH : Listings						
No.	Population	IDSL / TST ID / Example Shell	Title	Programming Notes	Report at Interim	Report at Final
Urinary Diary Data						
31.	FAS1	Study Specific	Listing of Urinary Diary Data		Y	Y
32.	FAS1	Study Specific	Listing of Derived Urinary Diary Data		Y	Y
Urodynamics Data						
33.	FAS1	Study Specific	Listing of Urodynamics Data		Y	
KHQ Data						
34.	FAS1	Study Specific	Listing of KHQ Data		Y	Y
Study Specific Safety Data						
35.	SPDB	Study Specific	Listing of PVR Data		Y	Y
36.	SPDB	Study Specific	Listing of CIC Data		Y	Y
37.	SPDB	Study Specific	Listing of Ultrasound		Y	Y
38.	SPDB	Study Specific	Listing of General Anesthesia		Y	Y

CONFIDENTIAL

204948

11.10.12. Patient Profile Listings

Patient Profiles: Listings					
No.	Population	IDSL / TST ID / Example Shell	Title	Programming Notes	Report at Final
CV Events					
39.	SPDB	IDSL standard	Listing of Investigator Reported Cardiovascular Events: Arrhythmias		If an event occurs
40.	SPDB	IDSL standard	Listing of Investigator Reported Cardiovascular Events: Congestive Heart Failure		If an event occurs
41.	SPDB	IDSL standard	Listing of Investigator Reported Cardiovascular Events: Cerebrovascular Events Stroke and Transient Ischemic Attack		If an event occurs
42.	SPDB	IDSL standard	Listing of Investigator Reported Cardiovascular Events: Deep Vein Thrombosis / Pulmonary Embolism		If an event occurs
43.	SPDB	IDSL standard	Listing of Investigator Reported Cardiovascular Events: Myocardial Infarction / Unstable Angina		If an event occurs
44.	SPDB	IDSL standard	Listing of Investigator Reported Cardiovascular Events: Peripheral Arterial Thromboembolism		If an event occurs
45.	SPDB	IDSL standard	Listing of Investigator Reported Cardiovascular Events: Pulmonary Hypertension		If an event occurs
46.	SPDB	IDSL standard	Listing of Investigator Reported Cardiovascular Events: Revascularisation		If an event occurs
47.	SPDB	IDSL standard	Listing of Investigator Reported Cardiovascular Events: Valvulopathy		If an event occurs
48.	SPDB	IDSL standard	Listing of Investigator Reported Events: Deaths		If an event occurs

CONFIDENTIAL

204948

11.11. Appendix 11: Example Mock Shells for Data Displays

Example mock shells will be provided as other document.

CONFIDENTIAL

204948

11.12. Appendix 12: How to identify the records for the interim analysis

This document defines the details how to apply the records to the interim analysis of BOTOX NDO 204948 from the released dataset(SIDATA), which includes the records won't be used for. Basically, described in the RAP, the records until 24weeks from the first treatment of each subject will be adopted for the analysis, however there are some data needed to be handled with particular handling rule. This document is provided to give a detailed description of these special handling rules as well as to suggest the physical structure of the analysis datasets from the aspect of data cutting.

Released data will be judged by record whether it should be included in the interim analysis or not, by comparing with the reference visit or date (Data cut visit or Data cut date) corresponding to 24 weeks of each subject. However, the Liver event and Cardiovascular event data will be decided for their adoption, by their specific rules described in chapter (2) and (3), instead of judgement by record.

(1) How to derive the reference visit or date (Data Cut Visit or Data Cut Date) corresponding to 24 weeks of each subject and the basic approach of judgement

Most of the records in SIDATA except for the records of Liver event or Cardiovascular event can be decided their adoption by comparing with the Data cut visit or Data cut date of each subject defined in below. Application of data cut type, i.e. visit or date, is determined by dataset considering its attribution. If the data is linked to particular visit in SIDATA, then it will be compared with Data cut visit by Visit number and will be adopted when it is smaller or equal to the reference. Data cut date will be used for the comparison with the relevant date of the logs data (i.e., AEs, conmeds, CIC etc.). The data up to or on Data cut date will be adopted.

The practical approach for each SIDATA will be described in chapter (4). Data cut visit(CUTVISIT), Data cut visit number (CUTVISN) and Data cut date(CUTDT) will be stored in ARDATA.MSTONE with Withdrawal until 24W (WDR24WFL), so that they can be used for the judgement in the process of ARDATA creation.

CONFIDENTIAL

204948

Condition 1	Condition 2		Data cut visit (Data cut visit number in 204947)	Data cut date
Withdrawn until 24W?	Last regular visit * ¹ of Treatment Cycle 1 In SIDATA.VISIT			
Subject without withdrawal until 24W DSCONT of 24w eq Y In DMDATA.DS	POST TX1 WEEK24 or later		POST TX1 WEEK24(170/300)	Visit date of the Data cut visit in SIDATA.VISIT, which will be imputed with “The date of first injection + 24 x 7” in the case of missing.
	POST TX1 WEEK18	treatment until 24w* ² : Twice	POST TX2 WEEK6(1020/1020)	
		treatment until 24w: Once	POST TX1 WEEK24(170/300)	
	POST TX1 WEEK12	treatment until 24w: Twice	POST TX2 WEEK12(1030/1100)	
		treatment until 24w: Once	POST TX1 WEEK24(170/300)	
Others besides		POST TX1 WEEK24(170/300)		
Subject withdrew until 24W			Last visit of the subject in SIDATA.VISIT	Visit date of the Data cut visit in SIDATA.VISIT

*1 : Regular visits are the visits named with “TX1”, except the ones for the assessment of re-treatment or qualification, i.e. the visits named with “-add” in 204947.

*2 : Treatment until 24w doesn't include the treatment just on 24w.

(2) How to make judgement of Liver Event data (with Visit number 8000s)

CONFIDENTIAL

204948

All of the liver event data (with Visit number 8000s) of the subject, to whom a liver event happens until 24W, will be adopted for the interim analysis. Whether the liver event happens until 24W or not will be judged by comparing the first detected date of liver event (LERSTDT in SIDATA.LEREPOR) and Data cut date of the subject, and if it starts before or equal to the reference date then the subject will be regarded with Liver event. This information will be stored in ARDATA.MSTONE as a variable of “Liver Event flag within w24 after 1st trt (LE24WFL)”.

(3) How to make judgement of Cardiovascular Event data (with Visit number 3000s)

None of the Cardiovascular Event data (with Visit number 3000s) will be used for the interim analysis. The patient profiles of CV events will be generated only at the end of the study, as defined in the display standard.

(4) The individual approach for the judgement of the adoption for the interim analysis

Following table shows the conditions to adopt the records for the interim analysis, which can be settled by dataset. The outcome of the judgement will be stored in a flag named as “Flag for interim analysis(ANLINTFL)” in each ARDATA. The records not used for the interim analysis will be included in ARDATA but will be excluded from the analysis by using “Flag for interim analysis”.

CONFIDENTIAL

204948

SIDATA	ARDAT A	English Description	Visit num <3000 or logs data	Visit num 8000s (liver event data)	Visit num 3000s (Cardiovascular event data)	Note
demo	demo	Demography	all	-	-	No data cut required
exposure	exposure	Exposure	VISITNUM<=CUTVISN	-	-	
ds	ds	Subject disposition	Adopt all records, except for the subject logs data (VISITNUM eq 0) of the subject who continued after 24w (MSTONE.WDR24WFL eq N).	-	-	Both of Visit data and logs data are involved
dv1	dv1	Protocol Deviations	DVSTDT <=CUTDT	-	-	
conmeds	conmeds	Concomitant medications	the records meet with any of following conditions will be adopted. 1) Compare the start date with the data cut date and adopt the	-	excluded	CV data can be identified with CONMEDS CMTYPCD eq 31

CONFIDENTIAL

204948

SIDATA	ARDAT A	English Description	Visit num <3000	Visit num 8000s	Visit num 3000s	Note
			
smaller or equal to (CMSTDT<=CUTDT) . CMSTDT needs to be imputed as in RAP definition. 2) the records with 'CMPRIOR eq Y' will be adopted.
 
For OAB
 
3) the records of prior medicine for OAB (CMTYPCD eq 25) will be adopted.
 
For NDO
 
3) the records of prior medicine for NDO (CMTYPCD eq 224) will be adopted.
			
	cmanal	Concomitant medications analysis dataset	-	-	--	Carry flags from conmeds
blind	blind	Status of Treatment Blind	all	-	-	No data cut required
elig	elig	Eligibility (inclusion/exclusi	all	-	-	No data cut required

CONFIDENTIAL

204948

SIDATA	ARDAT A	English Description	Visit num <3000	Visit num 8000s	Visit num 3000s	Note
		on)				
medhist	medhist	Medical History	all	If the subject's LE24WFL eq Y	excluded	
race	race	Collected race (check all that apply)	all	-	-	No data cut required
face	face	Findings About Clinical Event	VISITNUM<=CUTVISN	-	-	
khqking2	khqking2	Kings Health Questionnaire King-2	VISITNUM<=CUTVISN	-	-	
oabss	oabss	Overactive Bladder Symptom Score	VISITNUM<=CUTVISN	-	-	Only for OAB
tbsm	tbsm	Treatment Benefit Scale - Modified	VISITNUM<=CUTVISN	-	-	
ae	ae	Adverse Event	AESTDT <=CUTDT	-	-	
lab	lab	Laboratory Data	VISITNUM<=CUTVISN <LE related records> If the subject's LE24WFL eq Y and		excluded	Liver Events visit numbers 8000s are not used in LAB in the current standard.

CONFIDENTIAL

204948

SIDATA	ARDAT A	English Description	Visit num <3000	Visit num 8000s	Visit num 3000s	Note
			LAB.VISITDT is between LERSTDY and LERENDY of sidata.lereport			
ecg	ecg	ECG	VISITNUM<=CUTVISN	-	excluded	
vitals	vitals	Vital Signs Data	VISITNUM<=CUTVISN	-	excluded	
mo	mo	Morphology	VISITNUM<=CUTVISN	-		
surgery	surgery	Surgical procedures	SPDT<=CUTDT	-	excluded	
lereport	lereport	Liver event reporting	-	If the subject's LE24WFL eq Y	-	
subuse	subuse	Substance Use	all	If the subject's LE24WFL eq Y	-	
rucam	rucam	Liver Events RUCAM Scoring	-	If the subject's LE24WFL eq Y	-	
lbiopsy	lbiopsy	Liver Biopsy	-	If the subject's LE24WFL eq Y	-	
limaging	limaging	Liver Imaging	-	If the subject's LE24WFL eq Y	-	

CONFIDENTIAL

204948

SIDATA	ARDATA	English Description	Visit num <3000	Visit num 8000s	Visit num 3000s	Note
bacteria	bacteria	Bacteriology	VISITNUM<=CUTVISN	-	-	
ce	ce	Clinical Events	-	-	excluded	
cvdxtst	cvdxtst	Cardiovascular Events Diagnostic Tests	-	-	excluded	
dth	dth	Death event	DDDT<=CUTDT	-	-	
evidence	evidence	Physical Evidence	-	-	excluded	
facv	facv	Findings About Cardiovascular Events	-	-	excluded	
fadth	fadth	Findings About Death	all	-		
Famh	Famh	Findings about medical history	all			204948 only
Cc	CC		all			204948 only
EDSS	EDSS		all			204948 only

CONFIDENTIAL

204948

SIDATA	ARDAT A	English Description	Visit num <3000	Visit num 8000s	Visit num 3000s	Note
famhist	famhist	Family History	all	-		
hru	hru	Healthcare Resource Utilisation	-	-	excluded	
nyhascr	nyhascr	NYHA Score	-	-	excluded	
risk	risk	Risks Factors	-	-	excluded	
ss	ss	Subject Status	VISITNUM<=CUTVI SN	-		

(5) Special Notes

- If the date of the record of logs data is missing then it will be excluded from the analysis.
- In the comparison of visit number. If the data of Unscheduled Visit exists in the same visit number of Data cut visit, it will be adopted as far as its visit number is smaller than the Data cut visit number precisely. i.e. if Data cut visit number = 1020, data with 1020.1 will be excluded from the analysis.

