11.4.1.2. Study Phases for AE Data

Treatment State	Definition
Pre-Treatment	AE Start Date < Study Treatment Start Date
On-Treatment	If AE onset date is on or after treatment start date & on or before treatment stop date. Study Treatment Start Date \leq AE Start Date \leq Study Treatment Stop Date
Onset Time Since 1st Dose (Days)	If Treatment Start Date > AE Onset Date = AE Onset Date - Treatment Start Date If Treatment Start Date \leq AE Onset Date = AE Onset Date - Treatment Start Date +1 Missing otherwise.
Duration (Days)	AE Resolution Date – AE Onset Date + 1
Treatment Cycle 1 (TC1) \leq 84 days from 1st treatment	1st treatment Date \leq AE Start Date \leq 1st treatment Date +83
Treatment Cycle 1 (TC1)	1st treatment Date \leq AE Start Date (if the subject completes / withdraws without 2nd treatment) \leq Study Exit/Withdraw Date or (if the subject take 2nd treatment) < 2nd treatment Date

Treatment State	Definition
GSK1358820 Treatment Cycle 1 (GTC1)	For subjects who received GSK1358820 as 1st treatment: 1st treatment Date \leq AE Start Date (if the subject completes / withdraws without 2nd treatment) \leq Study Exit/Withdraw Date or (if the subject take 2nd treatment) $<$ 2nd treatment Date For subjects who received placebo as 1st treatment: 2nd treatment Date / Time \leq AE Start Date / Time (if the subject completes / withdraws without 3rd treatment) \leq Study Exit/Withdraw Date or (if the subject take 3rd treatment) $<$ 3rd treatment Date
GSK1358820 Treatment Cycle 2 (GTC2)	For subjects who received GSK1358820 as 1st treatment: 2nd treatment Date / Time \leq AE Start Date / Time (if the subject completes / withdraws without 3rd treatment) \leq Study Exit/Withdraw Date or (if the subject take 3rd treatment) $<$ 3rd treatment Date For subjects who received placebo as 1st treatment: 3rd treatment Date / Time \leq AE Start Date / Time \leq Study Exit/Withdraw Date
GSK1358820 Treatment Cycle 3 (GTC3)	For subjects who received GSK1358820 as 1st treatment: 3rd treatment Date / Time \leq AE Start Date / Time \leq Study Exit/Withdraw Date For subjects who received placebo as 1st treatment: Not applicable because 3 rd treatment of GSK1358820 is not allowed for subjects who received placebo as 1st treatment
Overall	For subjects who received GSK1358820 as 1st treatment 1st treatment Date \leq AE Start Date \leq Study Exit/Withdraw Date For subjects who received placebo as 1st treatment 2nd treatment Date \leq AE Start Date \leq Study Exit/Withdraw Date

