GTC2	Study Exit or Withdraw in TC2	Study Exit / Withdraw Date	2nd treatment date																													
GTC2	Receive next treatment	Date prior to 3rd treatment	2nd treatment date																													
GTC3	All subjects in GTC3	Study Exit / Withdraw Date	3rd treatment date																													

For subjects who received Placebo as first treatment
																																

Duration of Follow-Up instead of Extent of Exposure

Overall / TC for calculation	Subject status	X	Y
Overall	All subjects	Study Exit / Withdraw Date	2nd treatment date (1st treatment date of GSK1358820)
TC1	Study Exit or Withdraw in TC1	Study Exit / Withdraw Date [1]	1st treatment date
TC1	Receive next treatment	Date prior to 2nd treatment [1]	1st treatment date
GTC1	Study Exit or Withdraw in GTC1	Study Exit / Withdraw Date	2nd treatment date (1st treatment date of GSK1358820)
GTC1	Receive next treatment	Date prior to 3rd treatment	2nd treatment date (1st treatment date of GSK1358820)
GTC2	All subjects in GTC2	Study Exit / Withdraw Date	3rd treatment date (2nd treatment date of GSK1358820)
GTC3	Not applicable, because GSK1358820 treatment is allowed only two times for subjects who received Placebo as first treatment in this study.		

- [1] In interim analysis, use the following date:
 - Date of withdraw date for subjects who do not receive 2nd treatment and withdraw before week 24 after 1st treatment
 - Date of the Week 24 visit in treatment phase 1 for subjects who do not receive 2nd treatment and do not withdraw
 - Date prior to 2nd treatment for subjects who receive 2nd treatment at the Week 12 / 18 visit in treatment phase 1.

Duration of NDO history

- Duration of NDO history is defined as the duration (years) from the date of diagnosis to the date of screening visit.

Identification of anticholinergic drug and beta-3 agonist

- Since information of anticholinergic drug and beta-3 agonist was collected as 'prior NDO medication', it is needed to identify which codes will be regarded as anticholinergic drug and beta-3 agonist. Following code will be in SI dataset

Drug	Term Name	Code
Anticholinergics	FESOTERODINE	54026501
	FESOTERODINE FUMARATE	54026502
	IMIDAFENACIN	53735601
	OXYBUTYNIN	00538901
	OXYBUTYNIN HYDROCHLORIDE	00538902
	PROPIVERINE	01241601
	PROPIVERINE HYDROCHLORIDE	01241602
	SOLIFENACIN	53085701
	SOLIFENACIN SUCCINATE	53085702
	TOLTERODINE	01350201
	TOLTERODINE TARTRATE	01350202
	TOLTERODINE FUMARATE	01350203

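### For subjects who withdraw before Week 24 without a recorded final visit, the interim data cut stops at their last visit, so events between that visit and withdrawal drop out of the submission analysis

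*SAP*

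**What the plan says.** SAP 3.1 states that the interim is done for regulatory submission and uses data up to 24 weeks after first treatment. The opening of Appendix 12 (SAP 11.12) repeats that scope. Part (1) of the appendix then turns it into a cut visit and a cut date (CUTDT) for each subject.

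For a subject who withdrew by Week 24, the cut visit is "Last visit of the subject in SIDATA.VISIT" and the cut date is "Visit date of the Data cut visit in SIDATA.VISIT". Neither the withdrawal date nor the date of death enters.

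The cut date then governs everything not tied to a visit number: "Data cut date will be used for the comparison with the relevant date of the logs data (i.e., AEs, conmeds, CIC etc". The rule is that "The data up to or on Data cut date will be adopted". In the dataset table of part (4), the AE condition is "AESTDT <=CUTDT", and the death dataset is cut on date of death in the same way. Part (2) judges liver events against the same date: "if it starts before or equal to the reference date then the subject will be regarded with Liver event".

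SAP 11.6.2, note [1], sets the end of interim Treatment Cycle 1 follow-up differently: "Date of withdraw date for subjects who do not receive 2nd treatment and withdraw before week 24 after 1st treatment".

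**The concern.** The last visit and the withdrawal date need not coincide. A subject may die between visits, or leave without attending again. Protocol 7.4.1.1 collects AEs up to study exit and has SAEs reported within 24 hours, so events between visits do reach the database. Under Appendix 12 they are then flagged out of the interim if they start after the last visit.

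The records at risk are those closest in time to an unplanned withdrawal, and so the ones most likely to explain it. Because all disposition records are kept for these subjects, the submission could show a withdrawal while the event behind it is absent from the AE tables, the fatal SAE listing (Listing 18) and the listing of AEs leading to withdrawal (Listing 21). The follow-up tables would also count days on which events are not counted.

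**Working it through.** The plan gives no figure to reproduce here. The check is to apply the rule as written and compare it with the neighbouring rules.

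**1. Rules side by side, for a subject who withdraws before Week 24 without a second treatment**

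| Source | End of period |
|---|---|
| SAP 3.1 and opening of Appendix 12 | 24 weeks after first treatment |
| SAP 11.6.2 note [1], interim follow-up | withdrawal date |
| Appendix 12 (1), cut date for log data | date of last recorded visit |

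The third row is the earliest whenever no visit is recorded on or after withdrawal. For subjects who did not withdraw, Appendix 12 does give a calendar fallback, first injection + 24 x 7 days, if the visit date is missing. The row for withdrawn subjects has no such fallback.

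**2. Worked example (days assumed for illustration)**

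Last visit Day 43 (Week 6), fatal AE starts Day 55, death and withdrawal Day 60.

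- Current rule: CUTDT = Day 43. AE: 55 <= 43 is false, so it is dropped. Death record: 60 <= 43 is false, so it is dropped.
- Follow-up under SAP 11.6.2: 60 - 1 + 1 = 60 days. AEs are taken only to Day 43, so 60 - 43 = 17 follow-up days carry no events.
- Cut at the later of last visit and withdrawal: CUTDT = Day 60. 55 <= 60 and 60 <= 60 are true, so both records are kept.

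**3. How long the gap can be**

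Target days follow SAP 11.3.1, and visit windows are from the Time and Events Table (protocol 7.1). Longest gap = (later target + window) - (earlier target - window).

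| Contacts | Nominal (days) | Longest (days) |
|---|---|---|
| Week 0 to 2 | 15 - 1 = 14 | 18 - 1 = 17 |
| Week 2 to 6 | 43 - 15 = 28 | 50 - 12 = 38 |
| Week 6 to 12 | 85 - 43 = 42 | 92 - 36 = 56 |
| Week 12 to 18 | 127 - 85 = 42 | 134 - 78 = 56 |
| Week 18 to 24 | 169 - 127 = 42 | 176 - 120 = 56 |

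**4. Weight of one subject**

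With the planned 15 per arm, one subject is 1/15 = 6.7 percentage points of incidence. That is the most one dropped event can change for a given term; if the subject already has the same term earlier, incidence does not move.

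**5. Which displays are affected, and for how long**

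SAP Appendix 10 marks the Treatment Cycle 1 and Overall AE and SAE tables and Listings 15-22 for both interim and final, so the final run restores the events there. Tables 3.1-3.8, 3.53 and 3.54 (first 84 days) are marked for interim only. An event starting between the last visit and Day 84 would never be restored to those tables.

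**The case against.** The strongest reply is that the rule works in the planned case. The schedule has a dedicated Withdrawal visit that collects AEs and concomitant medication. The row for withdrawn subjects says "Last visit of the subject in SIDATA.VISIT" without limiting this to regular visits, so a recorded Withdrawal visit becomes the cut visit and little or nothing is lost. That stands. A reader might infer that every early withdrawal loses data; the documents do not support that.

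Nor is every unattended exit exposed. Appendix 12 treats Week 18, a telephone contact, as a regular visit in the visit dataset, so a withdrawal call may be stored as a visit too. For the same reason the 84 days from Week 12 to Week 24 should not be read as one unobserved gap. Subjects lost to follow-up are by definition out of contact, so they will seldom have later events to lose. What mainly remains is death, or withdrawal with no visit or call recorded.

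A reader might also infer that an arm's reported mortality could fall from one death in 15 to none. No interim display supports that. The death listing (Listing 48) is final-only, a fatal AE starting on or before the last visit passes the AE cut, and the disposition and findings-about-death records are kept. Listing 18 is affected only when the fatal AE itself starts in the gap.

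The definition of the Treatment Cycle 1 AE period (SAP 11.4.1.2), with its clause "if the subject completes / withdraws without 2nd treatment", may look like a further contradiction. It assigns events to cycles and runs to study exit for everyone not re-treated; it is not a data cut. The mismatch is with note [1] of SAP 11.6.2 and with the 24-week scope.

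Finally, the excluded records are flagged, not deleted, and most tables are rerun. That limits the harm but does not help the submission analysis or the 84-day tables.

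**Conclusion.** The point holds for a defined subgroup: subjects who withdraw before Week 24 with no visit recorded on or after the withdrawal date. For them Appendix 12, followed exactly, excludes records that lie inside the interim's own 24-week scope. For those without a second treatment, the excluded records also lie inside follow-up that the SAP counts. The excluded records are AEs, catheterization and concomitant-medication log entries, and liver events starting after the last visit.

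The size is up to 6.7 percentage points of an arm's incidence per affected subject, assuming 15 per arm. The exposed interval can be as long as 38 days between Weeks 2 and 6 and 56 days between later contacts. The documents do not show whether any subject is in this position, so the expected effect cannot be estimated. The error is temporary for tables rerun at the final analysis and lasting only for Tables 3.1-3.8, 3.53 and 3.54. It should be corrected because the interim supports the submission and the correction is simple.

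**What to change.** In Appendix 12 (1), for subjects withdrawn by Week 24, set CUTDT to the later of the last visit date and the study withdrawal date, using the date of death where death is the reason for withdrawal. Cap any extension beyond the last visit at first injection + 24 x 7 days. In symbols: CUTDT = max(last visit date, min(withdrawal or death date, first injection + 168 days)). This agrees with SAP 3.1 and with note [1] of SAP 11.6.2. Leave the visit-number cut for visit-based datasets unchanged.

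Removing the date cut altogether for these subjects would not be equivalent. Protocol 7.4.1.1 allows related SAEs and deaths learned of after discharge to be reported, and these could fall outside the 24-week scope. The cap is needed for the same reason.

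The cost is one line of SAP text and one line of programming, with no new data.

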3. PLANNED ANALYSES

3.1. Interim Analyses

The interim planned primary analyses will be performed after the completion of the following sequential steps:

1. All subjects have completed treatment phase 1 (or week 24 of treatment phase 1, except for the premature withdraw) as defined in the protocol.
2. If the subject completes treatment phase 1 and receives 2nd treatment, this subject should have completed the visit corresponding to 24 weeks after 1st treatment.
 - The subject who completed Week 12 visit and was re-treated at a visit before Week 18 in treatment phase 1 should complete the Week 12 visit in treatment phase 2.
 - The subject who completed Week 18 visit and was re-treated at a visit before Week 24 in treatment phase 1 should complete the Week 6 visit in treatment phase 2.
3. All required database cleaning activities have been completed and interim database release (DBR) and database freeze (DBF) has been declared by Data Management.
4. All criteria for unblinding the randomization codes have been met.
5. Randomization codes have been distributed according to RandAll NG procedures.

The interim analyses will be performed for regulatory submission. However subject level data will not be disclosed to people who work at the sites including investigators.

In interim analyses, the following analyses will be done with datasets which will include data until 24 weeks after 1st treatment.

- Study population
- Efficacy and safety analyses for treatment cycle (TC) 1 (except for time to event analyses)
- Safety analyses for Overall period (i.e., the analyses for population “SP1”, which include subjects who had at least one GSK1358820 treatment)

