NOTES:

- If the study withdraw date is missing then the AE will be considered to be On-Treatment.

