11.7.2.1. Handling of Missing and Partial Dates

Element	Reporting Detail
General	
 • Partial dates will be displayed as captured in subject listing displays.
Adverse Events	
 • The eCRF does not allow for the possibility of partial dates (i.e., only month and year) to be recorded for AE start and end dates • Completely missing start or end dates will remain missing, with no imputation applied. Consequently, time to onset and duration of such events will be missing. For example, this is the case for AEs status of ‘ongoing’ or AEs in interim analyses.
Concomitant Medications/ Medical History/NDO history	
 • Partial dates for any concomitant medications recorded in the CRF will be imputed using the following convention: 
 ○ If the partial date is a start date, a '01' will be used for the day and 'Jan' will be used for the month ○ If the partial date is a stop date, a '28/29/30/31' will be used for the day (dependent on the month and year) and 'Dec' will be used for the month. • The recorded partial date will be displayed in listings.

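### An adverse event with no start date drops out of the interim safety tables made for submission, and no rule places it in a period table at the final analysis either

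*SAP*

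**What the plan says.** SAP Appendix 12 (section 11.12) governs which records enter the interim analysis. Part (1) treats adverse events as log data and compares them with a subject-specific cut date: "Data cut date will be used for the comparison with the relevant date of the logs data (i.e., AEs, conmeds, CIC etc". The dataset table in part (4) gives the adverse event condition as "AESTDT <=CUTDT", which uses the start date only. Part (5) then adds: "If the date of the record of logs data is missing then it will be excluded from the analysis". Excluded records are not deleted: "The records not used for the interim analysis will be included in ARDATA but will be excluded from the analysis".

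SAP 3.1 states the purpose of this cut: "The interim analyses will be performed for regulatory submission".

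Two parts of the main SAP also bear on an undated event. Section 11.7.2.1 says: "Completely missing start or end dates will remain missing, with no imputation applied", and continues: "Consequently, time to onset and duration of such events will be missing". It adds that the eCRF does not accept partial adverse event dates. Section 11.4.1.2 defines the adverse event periods (first 84 days of TC1, TC1, GTC1 to GTC3, Overall), each by comparing the start date with treatment and exit dates. A note there covers a different missing item: "If the study withdraw date is missing then the AE will be considered to be On-Treatment".

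**The concern.** A blank field can remove a real event from the safety tables that go to the regulator. The event was probably post-treatment. Protocol 7.4.1.1 collects adverse events from the start of study treatment, lets earlier occurrences go into medical history, and records only related serious events from consent. What a blank start date usually leaves unknown is the cycle, and whether onset fell before the 24-week cut. Leaving the event out is not a cautious answer to either question.

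Protocol 9.4.2 plans to record all adverse events that occur during the study and to summarise them overall, by cycle and for the first 12 weeks. The SAP's table of changes from the protocol (section 2.1) does not mention this exclusion. With about 15 subjects per arm, one lost event is visible in an incidence table.

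**Working it through.** **1. Which events are lost at the interim.** Part (4) of Appendix 12 compares only the start date with the cut date. A blank start date cannot satisfy the condition, and part (5) confirms the exclusion. A missing end date plays no part, so an ongoing event is kept.

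**2. What happens at the final analysis.** Section 11.7.2.1 allows no imputation. Every period in 11.4.1.2 requires the start date to lie on or after a treatment date, and none has a fallback. An undated event therefore falls in no period, Overall included. If a query later supplies the date, the TC1 and Overall tables rerun at the final analysis would pick the event up. Tables 3.1 to 3.8 (adverse events in the first 84 days), 3.53 (serious events, same window) and 3.54 (special-interest events, same window) are marked for the interim only, so they have no final version in which it could reappear.

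**3. How the SAP treats other missing items.**
- Missing withdrawal date: the event counts as on-treatment (11.4.1.2).
- Missing causality: the event counts as related (11.6.4).
- Missing baseline urinalysis: assumed normal, so a later abnormality counts as an increase (8.3).
- Missing adverse event start date: excluded (Appendix 12) or in no period (11.4.1.2).

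The first three keep the safety signal; the last does not.

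**4. Weight of one subject.** SAP 8.1 says that one subject exceeds 5% in a group of about 15. This reproduces: 1/15 = 6.7%. For nearby group sizes, 1/13 = 7.7% and 1/17 = 5.9%. As an illustration, an arm with 3/15 (20.0%) would be shown with 2/15 (13.3%). The tables count subjects, so this loss arises only if the undated record is the subject's sole record of that event.

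**5. Effect on the comparison.** Take illustrative true counts of 3/15 on active and 2/15 on placebo, a difference of 1/15 = 6.7 points.
- Lose one active subject: 2/15 − 2/15 = 0 points.
- Lose one placebo subject: 3/15 − 1/15 = 13.3 points.

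Each arm's incidence can only fall, but the difference can shrink or grow.

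**6. How often.** The documents give no count of undated events. Assume E adverse event records by the cut, each with chance r of a blank start date. Then P(at least one exclusion) = 1 − (1 − r)^E.
- E = 20, r = 0.5%: 1 − 0.995^20 = 10%.
- E = 40, r = 1%: 1 − 0.99^40 = 33%.
- E = 60, r = 2%: 1 − 0.98^60 = 70%.

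Both E and r are assumptions. The width of the range shows that the documents do not settle the frequency.

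**The case against.** The strongest defence is that a record without a date cannot be shown to precede the cut, so leaving it out is an ordinary data-cut convention with little practical effect. Partial dates cannot be entered, required cleaning comes before the interim freeze (SAP 3.1), the record stays in the analysis dataset under a flag, and a listing of all adverse events is planned at the final analysis as well. All of that stands, and it is why the point is minor. It does not remove the exclusion, and it does not help the first-84-day tables.

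A reader might infer more than the documents support, in three ways.

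- *That Appendix 12 contradicts the main SAP.* It does not do so directly. Section 11.7.2.1 notes that onset time and duration will be missing and cites interim adverse events as an example, which reads as if the event is retained. But it never says that an undated event is counted, and 11.4.1.2 would leave it out of every period. The note on missing withdrawal dates concerns an event whose onset is known. The contrast with neighbouring rules is one of approach.
- *That any missing date removes an event.* Only the start date matters.
- *That the rule can only understate harm.* This holds for each arm's count, but not for the between-arm comparison, because the rule is blind to arm.

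The objection also limits the remedy. Placing every undated event in TC1 would be wrong for a subject given placebo and then re-treated with active before the cut. An event that arose on active could land in the placebo column of the only randomised comparison and narrow the difference.

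**Conclusion.** The concern holds in limited form. An adverse event with a missing start date is excluded from the interim analysis used for submission, and under the current definitions it enters no period table at the final analysis. The gap therefore runs through the SAP and is not confined to Appendix 12.

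The rule is less inclusive than the SAP's handling of other missing safety items. Each affected subject is worth about 6.7 points of incidence at 15 per arm, given that the lost record is that subject's only record of the event. The total effect cannot be computed from the documents and is probably small, because cleaning should leave few blank start dates. The change is worth making because it is cheap and the excluded event would otherwise go unreported in the tables.

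**What to change.** Exempt adverse events from the missing-date exclusion in Appendix 12 (5), and put the same rule into 11.4.1.2 so that it also governs the final analysis:

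1. Keep an adverse event with a missing start date unless its end date or reporting visit shows onset before first treatment or after the cut.
2. If the subject had received only one treatment by the cut, count the event in TC1, and also in GTC1 and Overall if that treatment was active.
3. If the subject had been re-treated, assign the cycle from the end date or reporting visit. If it is still unclear, count the event in the first active cycle and Overall, and not in the placebo TC1 column.
4. List these events and footnote their number in each affected table.

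The rule should also say whether such an event enters the first-84-day tables, since those have no final version.

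The cost is a few sentences in the SAP and a small programming change. The downside is that an event may occasionally be placed in the wrong cycle. Step 3 also leans against active when the cycle is unclear: for subjects given active first, the first active cycle coincides with TC1, while an unclear event in a re-treated placebo subject stays out of TC1. The footnoted count lets a reader judge whether this matters.
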